7.4 Third Study Encounter

At the completion of 24 weeks (\pm 14 days) post-index date, the Site Investigators and Subjects will be asked to complete the final study data collection

The Site Investigators will complete the following, based on the information documented in the corresponding patient medical charts, and per Subject interaction and per clinical judgment guided by observing study Subject via in-person or remote/virtual visit:

- IGA of AK status (in relation to baseline), and current severity of skin photodamage in the AK treated area on the face or scalp (using EPQ item).
- Investigator rating of overall appearance of the skin in the original AK treated area.
- Perceptions and satisfaction with different attributes of tirbanibulin, and future preference to re-treat with tirbanibulin (using ad hoc and EPQ items).
- Newly documented changes to patient's AK concomitant medications, as documented in medical charts in past 16 weeks since the Week-8 encounter.
 - Information of topical regimen used for re-treatment (since Week 8) and associated outcomes, if applicable.
 - In case of re-treatment with tirbanibulin:
 - AEs, ADRs and LSRs observed since the re-treatment, as documented in the medical charts.

- Information on withdrawal from study (if occurred within the past 16 weeks).

Subjects will be asked to complete a brief survey, via online survey portal or a mobile app, encompassing the following:

- Self-rating of overall appearance of the skin in the original AK treated area (using EPQ item).
- Self-rating of overall appearance of the skin in the new AK re-treated area (using EPQ item), if re-treated within past 16 weeks.
- Perceptions and satisfaction with different attributes of tirbanibulin (using TSQM-9 and EPQ items, where applicable), and future preference to re-treat with tirbanibulin.

Both the Site Investigators and Subjects will be thanked for their participation in the study. No specific study close-out tasks are expected of the study Subjects. Site Investigators will be asked to submit any outstanding data queries to the research team and then close out the study records at their respective sites.

7.5 AK Photography & Subject Insights

In a small subset of sites (up to 2), Site Investigators will utilize Canfield® photography equipment to take photographs of Subject's AK treated area in the face or scalp to visually capture the clinical status of AK at baseline (study entry) and at Weeks 1, 2, 4 and 8, and will document their assessment/grading of LSR. In addition to the baseline and Week-8 encounters, Subjects at these sites will hence be consented to undertake additional in-person visits at Weeks 1, 2 & 4. At Week 8, the Subjects from these sites will also be asked to record a 1-3 minute audio narrating their perceptions of treatment benefits associated with the tirbanibulin.

7.6 Early Termination Encounter (Study Encounter # x)

Site Investigators will attempt to follow the progress of every subject admitted to the study through to study completion. If a subject fails to complete requested study procedures (i.e, completion of online surveys, or complete study visits), a reasonable effort will be made to contact the subject and ascertain the reason(s) for non-compliance with study procedures.

If a subject does not complete the study for any reason (including Site Investigator discretion), the reason and circumstances for the subject's early termination will be documented; if possible, the assessments specified for the forthcoming (next) study encounter will be performed.

8 STUDY ASSESSMENTS

PROs, encompassing HRQoL, treatment satisfaction and elements from EPQ, will be assessed with study Subjects. Tirbanibulin treatment effectiveness and treatment satisfaction will be assessed by treating Site Investigators. Future treatment preferences will be assessed with both Subjects and Site Investigators. Safety will be evaluated in terms of AEs and ADRs during the treatment period. For pertinent measures, the study respondents will be given an option to indicate "don't know / not applicable", especially related to absence of information tied to a missing visit or Subject discontinuation from the study.

8.1 HRQoL Assessments

The Skindex 16 consists of 16 items that are classified into three domains: symptoms (four items), emotions, (seven items) and functioning (five items) (Chren 2012; Chren et al, 2001). The following questions (items) correspond to each subscale:

Scale	Items
Symptoms	1-4
Emotions	5-11
Functioning	12-16

All items are scored on a seven-point adjectival response scale, with a potential score of 0 to 6. A total score is the average of all 16 items and transformed to a liner scale of 100 varying from 0 (never bothered) to 100 (always bothered). A domain score is determined by the average of scores in each scale within the domain. The higher the score, the more severe is the impairment. The questionnaire will be administered in entirety, at baseline and at Week 8 post-index date.

8.2 Treatment Satisfaction Assessments

8.2.1 Study Subject Treatment Satisfaction Assessments

Treatment Satisfaction Questionnaire for Medication (TSQM-9) will be used to assess the treatment satisfaction of Subjects at Weeks 8 & 24 for all patients, in relation to the tirbanibulin treatment they received at the beginning of the study. TSQM-9 will measure patient satisfaction with treatment on three key domains, namely, effectiveness, convenience, and global satisfaction. The following questions (items) correspond to each subscale:

Scale	Items
Effectiveness	1-3
Convenience	4-6
Global satisfaction	7-9

Most items are scored on a 7-point Likert scale of: 1: very dissatisfied; 2: moderately dissatisfied; 3: slightly dissatisfied; 4: neutral; 5: slightly satisfied; 6: moderately satisfied; 7: very satisfied. Items 7 and 8 of TSQM-9 are scored on a 5-point scale of: 1: not at all confident/certain; 2: a little confident/certain; 3: somewhat confident/certain; 4: very confident/certain; 5: extremely confident/certain. TSQM subscale scores will be computed per tool owner specifications and transformed to scores ranging from 0 to 100, with higher scores representing higher satisfaction on respective domains. The TSQM-9 questionnaire will be administered in entirety, at Weeks 8, and 24 post-index date.

The TSQM-9 questionnaire will also be administered at Week 24 among Subjects who are retreated with tirbanibulin in the past 16 weeks (since Week 8 visit), to solicit their satisfaction with the most recent course of tirbanibulin treatment.

Subject's rating (at Weeks 8 & 24) of their satisfaction with the ability of tirbanibulin treatment to 'improve how their skin looks' and 'improve their skin texture' respectively, in the original treated area will be assessed. The responses will be solicited on the following 7-point Likert scale: 1: very dissatisfied; 2: moderately dissatisfied; 3: slightly dissatisfied; 4: neutral; 5:

slightly satisfied; 6: moderately satisfied; 7: very satisfied. These two EPQ items will also be administered at Week 24 again among Subjects who are retreated with tirbanibulin between Week-8 and Week-24 visits, to solicit their satisfaction with the respective attributes associated with the most recent course of tirbanibulin treatment.

Subject's rating of their 'overall satisfaction' with tirbanibulin treatment, in comparison to other topical treatment(s) will be assessed using a 5-point Likert scale of: 1: much worse; 2: somewhat worse; 3: same; 4: somewhat better; 5: much better. This 'overall satisfaction' assessment will be conducted among two Subject subgroups:

- Among Subjects who have experienced other topical treatments before start of tirbanibulin at baseline: At Week 8, compare rating of tirbanibulin treatment vs. previous topical treatment(s).
- Among Subjects who have been retreated with other topical treatments (other than tirbanibulin) between Week-8 and Week-24 visits: At Week 24, compare rating of original tirbanibulin treatment (at beginning of the study) vs. most recent topical treatment(s).

To complement the overall satisfaction question, factors associated with Subject's satisfaction rating will be assessed.

8.2.1 Site Investigator Treatment Satisfaction Assessments

An ad hoc satisfaction questionnaire very similar to TSQM-9 will be used to assess Site Investigators' satisfaction with tirbanibulin treatment at Weeks 8 & 24, in relation to the tirbanibulin treatment they administered to Subjects at the beginning of the study. The individual item and subscale scorings will be done similar to the original TSQM-9 questionnaire.

The same ad hoc questionnaire will also be administered at Week 24 among Site Investigators managing Subjects who are retreated with tirbanibulin in the past 16 weeks (since Week 8 visit), to solicit their satisfaction with the most recent course of tirbanibulin treatment.

Site Investigator's rating (at Weeks 8 & 24) of their satisfaction with the ability of tirbanibulin treatment to 'improve how their patient's skin looks' and 'improve their patient's skin texture' respectively, in the original treated area will be assessed. The responses will be solicited on the following 7-point Likert scale: 1: very dissatisfied; 2: moderately dissatisfied; 3: slightly dissatisfied; 4: neutral; 5: slightly satisfied; 6: moderately satisfied; 7: very satisfied. These two EPQ items will also be administered at Week 24 again among Subjects who are retreated with tirbanibulin between Week-8 and Week-24 visits, to solicit their satisfaction with the respective attributes associated with the most recent course of tirbanibulin treatment.

Site Investigator's rating of their 'overall satisfaction' with tirbanibulin treatment, in comparison to other topical treatment(s) will be assessed using a 5-point Likert scale of: 1: much worse; 2: somewhat worse; 3: same; 4: somewhat better; 5: much better. This 'overall satisfaction' assessment will be conducted among two Subject subgroups:

- Among Subjects who have experienced other topical treatments before start of tirbanibulin at baseline: At Week 8, compare rating of tirbanibulin treatment vs. previous topical treatment(s).
- Among Subjects who have been retreated with other topical treatments (other than tirbanibulin) between Week-8 and Week-24 visits: At Week 24, compare rating of original tirbanibulin treatment (at beginning of the study) vs. most recent topical treatment(s).

To complement the overall satisfaction question, factors associated with Site Investigator's satisfaction rating will be assessed.

8.3 Treatment Effectiveness Assessments

The effectiveness of tirbanibulin treatment will be assessed from the perspective of Site Investigators as well as the Subjects. It is expected that the Site Investigator assessments will be conducted via in-person visits/encounters at baseline, Week 8 and Week 24, and when in-person assessments are not feasible (owing to COVID-related travel restrictions), the assessments

maybe done via virtual/remote visits. The same evaluator at study site shall perform all evaluations for a subject during the study, as feasible.

8.3.1 *Investigator Global Assessment (IGA):*

Site Investigators to assess the status of subject's AK in the treated area on the face or scalp using the following IGA scale, at Weeks 8 and 24. The IGA should be representative of the investigator's overall general assessment of the subject's AK and take into account the quality, as well as the quantity, of AK lesions.

Outcome Measure	Score
Completely cleared - Approximately 100% clearance of AK lesions in the treated area	0
Partially cleared - Approximately $\geq 75\%$ clearance of AK lesions in the treated area	1
Moderately cleared - Approximately 50-74% clearance of AK lesions in the treated area	2
Minimally Cleared - Approximately <50% clearance of AK lesions in the treated area	3
Not Cleared - Approximately 0% clearance, i.e., all AK lesions remained in the treated area	4

8.3.2 *Severity of Skin Photodamage*

Site Investigators will be asked to rate the severity of skin photodamage in the AK treated area (at baseline, Weeks 8 and 24), on the following 4-point Likert scale:

Outcome Measure	Score
Absent - Smooth evenly pigmented skin	0
Mild - Freckling and/or other dyspigmentation	1

Moderate - Above plus mildly rough “dry” skin, fine wrinkling and/or telangiectasias or blotchy erythema	2
Severe - Above plus pronounced “dryness” and/or dyspigmentation and/or telangiectasia or erythema, and/or wrinkling, with or without areas of actinic purpura	3

8.3.3 Cosmetic Appearance of Skin

Subjects and Site Investigators will be asked to rate current ‘overall appearance of the skin’ in the AK treated area (at Weeks 8 and 24, in comparison to baseline), on the following 5-point Likert scale: 1: much worse; 2: somewhat worse; 3: no change; 4: somewhat improved; 5: much improved.

Subjects will be asked to state how often has he/she been bothered by the appearance of the skin, at Baseline and Week 8, using item # 7 in Skindex-16 questionnaire. This item however will not be analyzed individually but assessed as part of emotions subscale of Skindex-16.

8.3.4 Study Subject Qualitative Narratives

Subjects from a small subset of study sites (up to 2) will be asked to record a 1-3 minute audio (using the Mobile App) narrating their perceptions of treatment benefits associated with the tirbanibulin, at Week 8. This qualitative data will be used to ascertain attributes that study Subjects associate with tirbanibulin treatment in an un-prompted manner.

8.3.5 Study Subject Photographic Assessments

Site Investigators from a subset of study sites (up to 2) will take photographs of AK lesions in Subject’s treatment area on the face or scalp at baseline encounter and at Weeks 1, 2, 4 and 8, during the in-person visits. This photographic data will be used to document and depict the changes in AK lesions and LSRs that may be associated with tirbanibulin treatment in the study.

8.4 Additional Study Assessments

8.4.1 Future Treatment Preference

Subjects and Site Investigators will be asked to state their likelihood to consider tirbanibulin to retreat AK, on a 5-point Likert scale of: 1=very unlikely, 2=somewhat unlikely, 3=neutral, 4=somewhat likely, 5=very likely). This will be assessed at Weeks 8 and 24.

8.4.1 Convenience/Ease of Use

Subjects and Site Investigators will be asked to rate the convenience/ease of use associated with tirbanibulin treatment, in comparison to other topical treatment(s), using a 5-point Likert scale of: 1: much worse; 2: somewhat worse; 3: same; 4: somewhat better; 5: much better. This assessment will be conducted among two Subject subgroups:

- Among Subjects who have experienced other topical treatments before start of tirbanibulin at baseline: At Week 8, compare rating of tirbanibulin treatment vs. previous topical treatment(s).
- Among Subjects who have been retreated with other topical treatments (other than tirbanibulin) between Week-8 and Week-24 visits: At Week 24, compare rating of original tirbanibulin treatment (at beginning of the study) vs. most recent topical treatment(s).

8.4.2 Perceptions of LSRs

The following three assessments will be conducted at Week-8 for Subjects who have experienced other topical treatments before start of tirbanibulin at baseline, and at Week-24 for Subjects who have been treated with other topical treatments (other than tirbanibulin) between Week-8 and Week-24 visits:

- Subjects and Site Investigators will be asked to rate the ‘duration of skin reactions’ associated with tirbanibulin, in comparison to other topical treatments (previous or most recent retreatment). The relative assessment will be based on a 5-point Likert scale of: 1: much longer; 2: somewhat longer; 3: the same; 4: somewhat shorter; 5: much shorter.

- Subjects and Site Investigators will be asked to rate the ‘severity of skin reactions’ associated with tirbanibulin, in comparison to other topical treatments (previous or most recent retreatment). The relative assessment will be based on a 5-point Likert scale of: 1: much worse; 2: somewhat worse; 3: the same; 4: somewhat better; 5: much better.
- Subjects will be asked to rate the ‘impact on their daily activities due to skin reactions’ associated with tirbanibulin use, in comparison to other topical treatments (previous or most recent retreatment). The relative assessment will be based on a 5-point Likert scale of: 1: much worse; 2: somewhat worse; 3: the same; 4: somewhat better; 5: much better.

8.4.3 Unscheduled Patient Encounters

Number of unscheduled clinician encounters (via in-person clinic visits, telehealth visits and phone calls) that AK patient had in the past 8 weeks will be assessed, based on the information documented in the patient medical charts at Week 8 encounter.

8.4.4 Adherence to Treatment

Subjects will report (at Week 8) their adherence to tirbanibulin treatment by indicating the number of missed single-dose applications within the expected 5-day application period/regimen.

8.5 Safety Assessments

8.5.1 Definition of Adverse Events & Adverse Drug Reactions

An AE is any untoward medical occurrence in a patient administered a pharmaceutical product which does not necessarily have a causal relationship with this treatment. An AE can therefore be any unfavorable and unintended sign, symptom, or disease temporally associated with the use of a medicinal product, whether or not related to the medicinal product.

The Site Investigator will use the following terms to assess the severity of each AE:

- Mild: Awareness of symptoms or signs, but easily tolerated (acceptable)
- Moderate: Enough discomfort to interfere with usual activity (disturbing)
- Severe: Interferes significantly with ability to do work or usual activity (unacceptable)

A Serious Adverse Event (SAE) is any experience that suggests a significant hazard, contraindication, side effect or precaution. With respect to human clinical experience, this includes any event which:

- results in death,
- is life-threatening,
- requires inpatient hospitalization* or prolongation of hospitalization, unless hospitalization is for:
 - routine treatment or monitoring of the studied indication, not associated with any deterioration in condition.
 - elective or pre-planned treatment for a pre-existing condition that is unrelated to the indication under study and has not worsened since the start of study drug.
 - treatment on an emergency outpatient basis for an event not fulfilling any of the definitions of a SAE given above and not resulting in hospital admission.
 - social reasons and respite care in the absence of any deterioration in the subject's general condition.
- results in persistent or significant disability / incapacity, or
- is a congenital anomaly / birth defect,
- is a significant or important medical event that, based on appropriate medical judgment, may jeopardize the subject or may require intervention to prevent one of the other outcomes listed above.

* Hospitalization is defined as an overnight (in-patient) stay at the hospital or emergency room.

For all AEs (either related or not related to study medication), information about the outcome (i.e., recovered, recovering, not recovered, recovered with sequelae, fatal, unknown) and the action taken with the study treatment (i.e., drug withdrawn, dose reduced, dose increased, dose not changed, not applicable) will be documented.

Each AE, either serious or non-serious for which a causal relationship to tirbanibulin cannot be excluded, will be considered as an ADR. An ADR is an injury caused by taking medication. ADRs may occur following a single dose or prolonged administration of a medicinal product or

result from the combination of two or more medicinal products. LSRs (such as: erythema, flaking/scaling, crusting, swelling, vesiculation/pustulation, and erosion/ulceration), skin scarring and pigmentation (such as: hypo- and hyper-pigmentation) as a result of application of tirbanibulin in AK treatment area will not be considered as ADRs, but will be documented separately.

The determination of whether an AE is related to study treatment (tirbanibulin) will be based on information regarding the degree to which the study treatment had caused or contributed to the event and will be categorized per the following criteria:

- Related: There were good reasons and sufficient information (e.g. plausible time sequence, dose-response relationship, pharmacology, positive de-challenge and/or re-challenge) to assume a causal relationship with the study medication in the sense that it is plausible, conceivable or likely.
- Not Related: There were good reasons and sufficient information (e.g. implausible time sequence and/or attributable to concurrent disease or other drugs) to rule out a causal relationship with the study medication.

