The AK lesions may cause cosmetic discomfort and due to the premalignant nature of the condition, patients may fear developing skin cancer. This fear may affect patients' overall well-being by leading to anxiety and stress (Tennvall et al, 2015). Patients may feel embarrassed and frustrated with AK lesions located on the face (Esmann et al, 2007). Studies have shown that AK has negative impact on the patient's daily living activities and their Quality of Life (QoL) (Grada et al, 2021), and presence of higher AK lesion counts on the face have been shown to be associated with worse skin-related quality of life among AK patients (Siegel et al, 2017; Emilio et al, 2016). AK treatments are associated with different levels of local skin reactions (LSRs) such as erythema, swelling, erosion, crusts, scaling, itching and burning sensation (Jansen et al, 2019), and such negative experiences with treatment may adversely impact the future willingness to retreat and treatment adherence among AK patients that can lead to poor outcomes in long term (Balcer et al, 2019; Del Rosso et al, 2014; Goldberg, 2017; Rosso et al., 2021). Therefore,

it is important to incorporate PROs that provides patient perspectives and provides important supplement to efficacy and safety data for the treatment(s), showcasing their complete value proposition.

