Each AE, either serious or non-serious for which a causal relationship to tirbanibulin cannot be excluded, will be considered as an ADR. An ADR is an injury caused by taking medication. ADRs may occur following a single dose or prolonged administration of a medicinal product or result from the combination of two or more medicinal products. LSRs (such as: erythema, flaking/scaling, crusting, swelling, vesiculation/pustulation, and erosion/ulceration), skin scarring and pigmentation (such as: hypo- and hyper-pigmentation) as a result of application of tirbanibulin in AK treatment area will not be considered as ADRs, but will be documented separately.

The determination of whether an AE is related to study treatment (tirbanibulin) will be based on information regarding the degree to which the study treatment had caused or contributed to the event and will be categorized per the following criteria:

- Related: There were good reasons and sufficient information (e.g. plausible time sequence, dose-response relationship, pharmacology, positive de-challenge and/or re-challenge) to assume a causal relationship with the study medication in the sense that it is plausible, conceivable or likely.
- Not Related: There were good reasons and sufficient information (e.g. implausible time sequence and/or attributable to concurrent disease or other drugs) to rule out a causal relationship with the study medication.

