LSR3 Crusting (N=X)			
Grade			
Mild	n (%)	n (%)	n (%)
Moderate	n (%)	n (%)	n (%)
Severe	n (%)	n (%)	n (%)
Action taken with Tirbanibulin			
Drug withdrawal	n (%)	n (%)	n (%)
Dose Reduced	n (%)	n (%)	n (%)
Dose Increased	n (%)	n (%)	n (%)

Dose not changed	n (%)	n (%)	n (%)
Not Applicable	n (%)	n (%)	n (%)

LSR4 Swelling (N=X)**Grade**

Mild	n (%)	n (%)	n (%)
Moderate	n (%)	n (%)	n (%)
Severe	n (%)	n (%)	n (%)

Action taken with Tirbanibulin

Drug withdrawal	n (%)	n (%)	n (%)
Dose Reduced	n (%)	n (%)	n (%)
Dose Increased	n (%)	n (%)	n (%)
Dose not changed	n (%)	n (%)	n (%)
Not Applicable	n (%)	n (%)	n (%)

LSR5 Vesiculation/Pustulation (N=X)**Grade**

Mild	n (%)	n (%)	n (%)
Moderate	n (%)	n (%)	n (%)
Severe	n (%)	n (%)	n (%)

Action taken with Tirbanibulin

Drug withdrawal	n (%)	n (%)	n (%)
Dose Reduced	n (%)	n (%)	n (%)
Dose Increased	n (%)	n (%)	n (%)
Dose not changed	n (%)	n (%)	n (%)
Not Applicable	n (%)	n (%)	n (%)

LSR6 Erosion/Ulceration (N=X)**Grade**

Mild	n (%)	n (%)	n (%)
Moderate	n (%)	n (%)	n (%)
Severe	n (%)	n (%)	n (%)

Action taken with Tirbanibulin

Drug withdrawal	n (%)	n (%)	n (%)
Dose Reduced	n (%)	n (%)	n (%)
Dose Increased	n (%)	n (%)	n (%)
Dose not changed	n (%)	n (%)	n (%)

Not Applicable	n (%)	n (%)	n (%)
LSR7 Scarring			
Present?			
Yes	n (%)	n (%)	n (%)
No	n (%)	n (%)	n (%)
LSR8 Hypo-pigmentation			
Present?			
Yes	n (%)	n (%)	n (%)
No	n (%)	n (%)	n (%)
LSR9 Hyper-pigmentation			
Present?			
Yes	n (%)	n (%)	n (%)
No	n (%)	n (%)	n (%)

Table 4.14 Subject Level Summary of Local Site Reactions, by Patient ID

Patient ID	Study/ Survey Timepoint	LSR	Grade	Date of Baseline (yyyy/mm/dd)	Date of Onset (yyyy/mm/dd)	Status	Action Taken with tirbanibulin*

Table 4.15 Subject Level Summary of Adverse Events, Any Type

Adverse Events, Any Type	N=X n (%)
Subjects with at least 1 adverse event (any type)	
Intensity of adverse event, among Subjects with at least 1 adverse event (any type)	
Mild	
Moderate	
Severe	
Action taken with Tirbanibulin, among Subjects with at least 1 adverse event (any type)	
Drug withdrawal / study discontinuation	
Other Actions:	
Dose Not Changed	
Subjects with at least 1 SAE or Serious ADR	
Subjects with at least 1 SAE or Serious ADR resulting in death	

Table 4.16 Subject Level Summary of 'Not-Related to Tirbanibulin' Adverse Events

'Not-Related to Tirbanibulin' Adverse Events	N=X n (%)
Subjects with at least 1 'not-related' AE	
Intensity of adverse event, among Subjects with at least 1 'not-related' AE	
Mild	

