Moderate	
Severe	
Action taken with Tirbanibulin, among Subjects with at least 1 'not-related' AE	
Drug withdrawal / study discontinuation	
Other Actions:	
Dose Not Changed	
Subjects with at least 1 SAE	
Subjects with at least 1 SAE resulting in death	

Table 4.17 Subject Level Summary of 'Not-Related' AEs by Organ Class & Preferred Term

System Organ Class: Preferred Term	N=X	Intensity	Action Taken
	n (%)	Mild, Moderate, Severe	A: Dose not changed; B: Drug withdrawn.

Table 4.18 Subject Level Summary of Adverse Drug Reactions

Adverse Drug Reactions	N=X n (%)
Subjects with at least 1 ADR	
Intensity of adverse event, among Subjects with at least 1 ADR	
Mild	
Moderate	
Severe	
Action taken with Tirbanibulin, among Subjects with at least 1 ADR	
Drug withdrawal / study discontinuation	
Other Actions:	
Dose Not Changed	
Subjects with at least 1 Serious ADR	
Subjects with at least 1 Serious ADR resulting in death	

Table 4.19 Subject Level Summary of ADRs by Organ Class & Preferred Term

System Organ Class: Preferred Term	N=X	Intensity	Action Taken
	n (%)	Mild, Moderate, Severe	A: Dose not changed; B: Drug withdrawn.

Table 4.20 Subject Level Summary of Serious ADRs by Organ Class & Preferred Term

System Organ Class: Preferred Term	N=X	Intensity	Action Taken
	n (%)	Mild, Moderate, Severe	A: Dose not changed; B: Drug withdrawn.

Table 4.21 Event Level Summary of Adverse Events, Any Type

Adverse Events, Any Type	N=X n (%)
Total number of adverse event (any type)	
Intensity of adverse event, among documented adverse events (any type)	
Mild	
Moderate	
Severe	
Action taken with tirbanibulin, for documented adverse events (any type)	
Drug withdrawal / study discontinuation	
Other Actions:	
Dose Not Changed	
Number of SAEs or Serious ADRs	
Number of SAEs or Serious ADRs resulting in death	

Table 4.22 Event Level Summary of 'Not-Related to Tirbanibulin' Adverse Events

'Not-Related to Tirbanibulin' Adverse Events	N=X n (%)
Total number of 'not-related' AE	
Intensity of adverse event, among documented 'not-related' AEs	
Mild	
Moderate	
Severe	
Action taken with tirbanibulin, for documented 'not-related' AEs	
Drug withdrawal / study discontinuation	
Other Actions:	
Dose Not Changed	
Number of SAEs	
Number of SAEs resulting in death	

Table 4.23 Event Level Summary of 'Not-Related' AEs by Organ Class & Preferred Term

System Organ Class: Preferred Term	N=X	Intensity	Action Taken
	n (%)	Mild, Moderate, Severe	A: Dose not changed; B: Drug withdrawn.

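### Local skin reactions are excluded from ADRs even when serious, so a zero in the Serious ADR tables would not mean that no serious drug-caused reaction occurred

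*Protocol*

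**What the plan says.** Protocol 8.5.1 starts broadly. Any AE, serious or non-serious, "for which a causal relationship to tirbanibulin cannot be excluded, will be considered as an ADR". It then takes out a group of reactions, "LSRs (such as: erythema, flaking/scaling, crusting, swelling, vesiculation/pustulation, and erosion/ulceration), skin scarring and pigmentation", saying that when these arise from the treatment they "as a result of application of tirbanibulin in AK treatment area will not be considered as ADRs, but will be documented separately". SAP 5.6.1 carries the same rule: "tirbanibulin in AK treatment area will not be considered as ADRs, but will be documented separately". Neither text limits the exclusion to non-serious cases.

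The AE and SAE definitions in 8.5.1 contain no LSR exception. Protocol 8.5.2 requires any AE that meets the SAE definition to be entered in the eDCF, documented on the Safety Report Form and sent to the sponsor within one working day.

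In SAP 7.4, Tables 4.15 and 4.21 summarise AEs of any type. Below them there are two branches, AEs not related to tirbanibulin and ADRs. Serious events have their own organ-class and preferred-term tables only in the ADR branch, for example "Table 4.20 Subject Level Summary of Serious ADRs by Organ Class & Preferred Term". LSRs are summarised in Table 4.13 and listed in "Table 4.14 Subject Level Summary of Local Site Reactions, by Patient ID".

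On what counts as an LSR, Protocol 2.1 describes AK treatments as causing "local skin reactions (LSRs) such as erythema, swelling, erosion, crusts, scaling, itching and burning sensation".

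**The concern.** Safety and tolerability is a stated objective, LSR frequency is a named endpoint, and Protocol 2.1 presents milder LSRs as an advantage of the drug. Readers will go to the Serious ADR tables to see whether the drug caused serious harm. For a topical treatment, the application site is a natural place for such harm to arise, and the rule removes that class of event from those tables whatever its consequences. A patient with drug-caused ulceration leading to admission would, on a literal reading, have a serious reaction caused by tirbanibulin that is not a Serious ADR.

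The second issue is consistency. The exclusion works through examples, so two sites could classify application-site itch or burning differently, and the ADR rate would then depend partly on site habit.

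**Working it through.** The plan gives no event rate or sample size calculation on this point, so there is no stated figure to reproduce. The check is to follow one serious, tirbanibulin-caused LSR through the SAP 7.4 tables.

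| Table | Is it counted? | Why |
|---|---|---|
| 4.13 | Yes, if it is one of the nine types, but not as serious | LSR1 to LSR6 have severity grade and action taken; LSR7 to LSR9 have yes/no only |
| 4.14 | Can be listed, not marked serious | Columns cover type, grade, dates, status and action; none for seriousness |
| 4.15, 4.21 | It can be | Rows cover SAEs or Serious ADRs of any type |
| 4.16-4.17, 4.22-4.24 | No | Not-related events only |
| 4.18-4.20, 4.25-4.28 | No | ADRs only, and the rule says an LSR is not one |
| 4.29-4.30 | Cannot be determined | Content is not defined |

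Three observations follow.

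1. The grade in Table 4.13 does not stand in for seriousness. Severe in 8.5.1 means significant interference with work or usual activity; serious means death, admission, disability and the like.
2. The listings for not-related AEs (4.24) and ADRs (4.28) both have a column asking whether the event is an SAE. The LSR listing (4.14) does not.
3. If serious LSRs are in the any-type total, their number could be found at event level by subtraction: the serious count in 4.21, minus that in 4.22, minus that in 4.25. The result carries no event type. Subject-level subtraction (4.15, 4.16, 4.18) need not work, because one patient can have events in more than one class.

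Scale, using the Safety Population of 300 given in SAP section 7:

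- One serious LSR: 1/300 = 0.33%, against 0/300 in the Serious ADR tables.
- The chance of at least one case is 1 − (1 − p)^300. For assumed true rates of 0.1%, 0.5% and 1% this is 25.9%, 77.8% and 95.1%.
- A reader who sees 0/300 may attach a one-sided 95% upper limit of 1 − 0.05^(1/300) = 0.99%. That limit would not apply to serious drug-caused reactions as a whole if LSRs are excluded from the numerator.

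For the clarification on wording, Protocol 2.1 names seven LSR examples: erythema, swelling, erosion, crusts, scaling, itching and burning. Table 4.13 has nine rows: the six signs of 8.5.1, scarring, hypo-pigmentation and hyper-pigmentation. Five of the seven examples have a row; 7 − 5 = 2 do not, itching and burning. There is no row for pain or for other LSRs. If 5% to 15% of patients had such symptoms (an assumption), 0.05 × 300 = 15 to 0.15 × 300 = 45 patients would be open to differing classification.

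**The case against.** A reader might infer that a serious LSR can disappear from the safety tables altogether. The documents do not support that. The exclusion is from ADRs only, 8.5.2 still requires recording and expedited reporting of every SAE, and Tables 4.15 and 4.21 can count the event. Serious ulceration also has its own row in Table 4.13 (LSR6), with grade and action taken. Reporting LSRs apart from ADRs is an explicit choice, disclosed in both documents.

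A reader might also infer that itch and burning appear in no table. That too goes further than the text. Protocol 2.1 is a background sentence about AK treatments in general. The operational wording in 8.5.1 and SAP 5.6.1 does not name itch or burning, and the items it does name match the nine rows of Table 4.13. A site could properly record burning as an AE, and as an ADR when related. Table 4.14 has an open LSR column, and the annotated CRF to which Table 4.13 refers is not among the documents, nor is the Safety Reporting Plan.

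These points limit the concern but do not remove it. Being counted in an any-type total, or graded in an LSR table, does not identify an event as both serious and caused by the drug. No table below the any-type level does that for an LSR. The SAP also does not say whether events on the LSR page feed the any-type tables.

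**Conclusion.** The point holds for the Serious ADR tables. If the plan is followed exactly, a serious tirbanibulin-caused LSR is reportable as an SAE and can enter the any-type totals, but it falls outside both branches below them and is not marked serious in the LSR tables. A zero for Serious ADRs would therefore be a zero for non-LSR reactions only.

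The number affected is probably small and cannot be estimated from the documents. One case moves the rate from 0 to 0.33%. The assumed rates of 0.1% to 1% show scale only, as does the 5% to 15% range for itch, burning or pain. The conclusion rests on the rules as written and does not depend on these rates. It could be eased by eDCF instructions that are not in the documents.

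The itch and burning issue is a secondary wording clarification.

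**What to change.** 1. In Protocol 8.5.1 and SAP 5.6.1, add that any LSR, scarring or pigmentation event that meets an SAE criterion is also entered on the AE page and counted in the Serious ADR tables.
2. Add to Table 4.14 the same SAE column that Tables 4.24 and 4.28 already have.
3. As a clarification, replace the open example list with the nine items that have a row in Table 4.13. State that other application-site reactions, such as itch, burning or pain, are recorded as AEs, and as ADRs when related. Alternatively, keep the list open and add a row for other LSRs to Table 4.13.

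The cost is a few sentences in two documents and one listing column. The reported ADR and Serious ADR rates may become slightly less favourable. SAP 7.4 describes the 300 patients as having already started the study, so if data are already collected, some sites may need to be queried retrospectively about the seriousness of recorded LSRs.
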